#### **STATISTICAL ANALYSIS PLAN**

The research coordinators will collect data on a hard copy source document. Clinical and laboratory data will then be entered into an Access database by the coordinator and lab personnel.

The data will be analyzed using SAS 9.4 software. All statistical tests will be two-sided with a significance level of 0.05. Patients who withdraw while on treatment will be included in the data analysis for each time point before withdrawal. Baseline and follow-up measurements of safety, tolerability, numbers of pathogenic bacteria, wound infection persistence or worsening, and gross effects on the rate of wound healing will be summarized using descriptive statistics such as mean, median, standard deviation, interquartile range, frequency, and percentage where appropriate. Normality assessments for the continuous variables will be completed using Shapiro-Wilk tests and stem-and-leaf plots.

Tests of equivalence between the TheraGauze + tobramycin and standard iodoform wick packing treatment groups will establish statistical significance if the two-sided 90% confidence

interval for the difference falls within the limits  $(-\delta, \delta)$ , where  $\delta$  is the margin of clinically accepted difference. This analysis will determine whether the outcomes are equivalent between the TheraGauze+tobramycin and standard iodoform wick packing treatment groups.

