Protocol Title: Safety and Tolerability Study of Antimicrobial TheraGauze for Skin Abscess - Pilot Study

Phase of Study: I

Version date: 30March2017

Funding for this project is from the Department of Defense, through Soluble Systems, LLC

Principle Investigator: [name]  
Eastern Virginia Medical School  
[name]  
[name]  
[contact]  
[contact]  
[contact]  
Email: [[contact]](mailto:[contact])

Institutional Review Board: Eastern Virginia Medical School IRB (FWA00003956)

**Background.** Skin infections resulting in abscess, furunculosis, have become increasingly common in the past decade with the rapid emergence of community-associated methicillin-resistant *Staphylococcus aureus* (MRSA). The increasing incidence of these skin infections has stressed the medical system at the primary care, urgent and emergent care levels at significant cost. Methicillin-resistant *S. aureus* (MRSA) killed 18,650 Americans in 2005, exceeding the number of deaths attributable to HIV/AIDS (Klevens, Morrison et al. 2007). MRSA infections were identified for 368,600 hospital stays in the U.S. in 2005 for an estimated \$5 billion in hospitalization costs (Healthcare Cost and Utilization Project, DHHS).

The primary endpoint of the study is to evaluate the safety of and identify side effects of TheraGauze/tobramycin wound packing compared with standard of care management for cutaneous abscesses requiring incision and drainage. Current standard of care in most emergency and urgent care settings for community-acquired skin abscess is incision and drainage followed by packing with cotton wick ( $\pm$  iodoform) and anti-MRSA systemic antibiotics given orally for 5 – 7 days (Mistry, Weisz et al. , LoVecchio, Perera et al. 2009). Commonly prescribed oral antibiotic regimens include trimethoprim-sufamethoxazol, doxycycline, and clindamycin. Common side effects from these systemic antibiotics include diarrhea (~20%), nausea, and rash (Powell and Wenzel 2008). Uncommon but severe side effects include *C. difficile* colitis, Stevens-Johnson Syndrome, toxic epidermal necrolysis, hepatitis, and aplastic anemia (Bell, Foster et al. , Mistry, Schwab et al. 2009).

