## Methods.

### Design:

This is a proof-of-concept, prospective, randomized clinical trial for safety of TheraGauze-tobramycin in adult subjects who present to Emergency Department settings for care of skin abscess requiring incision and drainage. A control, standard of care, arm is included to provide some data with respect to the side effect profile of current furunculosis management for comparison.

Two arms are proposed for this study:

1. Incision + TheraGauze+tobramycin packing (no systemic antibiotics)
2. Incision + standard iodoform wick or plain cotton wick packing ( $\pm$  p.o. antibiotics)

Anti-microbial TheraGauze (saturated with tobramycin ophthalmic solution at 3 mg/ml) will be packed into the drained wounds of the subjects in the study arm. The control arm will receive current standard of care wound packing with a choice of iodoform wick or plain cotton wick, based on the preference of the ED physician. After packing, the wound excess TheraGauze or wick will be cut away. The ED physicians have the option to prescribe an oral antibiotic or not,

according to their preference. The following oral antibiotic choices are available for subjects in the control arm only:

- Bactrim (TMP/SMX)
- Vibramycin (doxycycline)
- Cleocin (clindamycin)

Antibiotics will be purchased by subjects from their local pharmacy.

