#### Methods:

*Study Population:*

Subjects from the Hampton Roads region of southeastern Virginia will be recruited from the hospital emergency department site staffed by EVMS physicians at Sentara Norfolk General Hospital.

*Study Size:*

We anticipate screening 200 patients in order to enroll and randomize 100 subjects. Subjects will be randomized 2:1 to the TheraGauze+tobramycin or iodoform wick/ plain cotton wick, respectively. We anticipate 50 participants completing the study. The 50% retention rate is typical for emergency department populations.

*Subject Eligibility:*

Inclusion criteria:

- Ages  $\geq 18$  to  $\leq 65$  years at time of enrollment
- Subject has skin abscess (furuncle) requiring incision and drainage
- Erythema surrounding abscess
- Induration of  $\geq 2$ cm in maximal diameter
- Fluctuance or purulent head evident
- Tenderness at abscess
- No or mild fever  $\leq 38.5^{\circ}\text{C}$
- Male or female
- Ability to read and understand the English language at a level sufficient to provide informed consent and comply with study requirements
- Subject is willing and able to comply with all study requirements

Exclusion criteria:

- Systemic illness or deep-seated infection requiring inpatient admission (i.e. hypotension, tachycardia, or tachypnea)
- Deep seated infection requiring referral to surgery
- Subject requires intravenous antibiotics for suspicion of systemic spread of infection (i.e. suspicion of bacteremia)
- Extensive cellulitis extending  $> 6$ cm beyond the area of induration
- Fever  $> 38.5^{\circ}\text{C}$
- Allergy to any aminoglycoside antibiotic, sulfamethoxazole-trimethoprim, doxycycline, clindamycin.
- An underlying medical condition that impairs normal immune function (e.g. AIDS, cancer, diabetes, lupus, rheumatoid arthritis, organ or marrow transplantation, ulcerative colitis, Crohn's disease)
- Subject is pregnant or breastfeeding and/or a woman of childbearing potential who is not surgically sterile, not at least 2 years postmenopausal, or does not practice contraception methods, unless sexually abstinent for the duration of the study.
- Subject has any medical or psychiatric condition, in the opinion of the investigator, could jeopardize the subject's health or compromise the subject's ability to participate in the study.
- Subject has prior treatment with antibiotics in the preceding 7 (seven) days.

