- Currently taking or has taken oral or injection steroid medication (e.g. prednisone or Medrol Dosepak) in the past 30 (thirty) days

- Injection medications (Remicade, Humira, Cimzia, Simponi) other than vitamin (B6)
- Currently taking or has taken immune suppressing medications (e.g. methotrexate, Prograf, CellCept, Rapamune) in the past 30 (thirty) days
- Currently taking or has taken medications to treat cancer in the past 30 (thirty) days
- Subject is currently participating or has participated within the last two months in any study of an investigational drug or device.

*Recruitment and Retention:*

Subjects who present to Emergency Department setting for care of skin abscess requiring incision and drainage will be approached by on-site Study Coordinators for enrollment. The study coordinators and physician investigators are trained in obtaining informed consent. The potential subjects will be able to discuss participation with any family-member present, but due to the need for prompt treatment, the subject will need to make a decision regarding participate at the time of the Emergency Room visit. Upon meeting eligibility criteria and willingness to participate, subjects/LARs will provide informed consent. Complete demographic information to include residential and telephone contact information will be obtained. Prior relevant medical history and usual primary care contact information will also be collected. A medical information release will be obtained from the subject so that outcomes data can be collected related to additional unscheduled visits or adverse events cared for outside the emergency department setting.

*Women and minority participation:*

Adults up to 65 years of age will be enrolled regardless of gender and minority status as long as they are fluent in English.

*Randomization:*

A study subject identification number will be assigned. Subjects will then be sequentially randomized to one of two treatment arms upon enrollment in a 2:1 ratio, using a prepared list. Each subject's name will be recorded on the list next to his/her assigned subject number and randomization. For example, the first subject enrolled will be randomized to Treatment 1; the next enrolled subjects will be enrolled to Treatment 1; the third subject to Treatment 2. The fourth subject will be randomized to Treatment 1 and so on.

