**Study Treatments**

Visit 1 - Day 1:

- Informed consent will be obtained from subject.
- Review of Eligibility Criteria (Inclusion/Exclusion)
- Randomization to Treatment Arm
- Contact Information to include phone number(s), address, and primary care provider information will be collected.
- Treatment and discharge with instructions to return to the ED for reevaluation per routine care. The typical schedule is for the patients to return to the ED 2 days after initial wound care (Study Day 3 -1/+2).

The following information will be collected and recorded on a hard copy Case Report Form at this visit.

- Subject ID number
- Demographics

- Date of visit
    - Age in years and months at time of enrollment
    - Race (white, non-white)
    - Ethnicity (Hispanic or non-Hispanic)
  - Medical history
    - Chronic medical conditions:
      - \_\_\_\_\_
      - \_\_\_\_\_
      - \_\_\_\_\_
      - \_\_\_\_\_
    - Concomitant Medications
      - \_\_\_\_\_
      - \_\_\_\_\_
      - \_\_\_\_\_
      - \_\_\_\_\_
    - Allergies to medications
      - \_\_\_\_\_
      - \_\_\_\_\_
      - \_\_\_\_\_
  - Characteristics of symptoms and history
    - Duration of symptoms (number of days)
    - Fever > 38.0°C duration? (y/n, record number of days febrile at home prior to ED visit)
    - Fever > 38.0°C in ED? (y/n, record temp)
    - Spontaneous drainage (y/n)
    - Prior skin abscess (y/n)
    - Immediate family history (parent, sibling, child) of skin abscess (y/n)
  - Abscess characteristics
    - Erythema at widest diameter (mm)
    - Abscess induration at widest diameter (mm)
    - Abscess location (e.g. trunk, extremity, buttocks, perineal, axilla, head/neck)
  - Procedure information
    - Diameter of wound after incision (mm)
    - Treatment Arm:
      1. Anti-microbial TheraGauze (TheraGauze/tobramycin)
      2. Iodoform wick/ plain cotton wick
    - Length of packing used (mm)
  - Laboratory Assessments – Per standard clinical care the abscess contents will be sent for routine Gram stain, bacterial culture and susceptibility testing as dictated by the patient's insurance and ED policy.
    - Obtain results when available
  - If patient is to receive iodoform wick/plain cotton wick then the care provider will have the option of prescribing a p.o. antibiotic, as is frequently done in these clinical settings. The following oral antibiotic choices are available for subjects in the control arm only:
    - Bactrim (TMP/SMX)
    - Vibramycin (doxycycline)

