    - Cleocin (clindamycin)

Phone Follow up Contact Day 2 (+2)

Return visit reminder and wound status follow up performed by Sentara Study Coordinator.

- Questions
  - Fever since leaving ED? (y/n, record temp if taken)
  - If prescribed, was antibiotic prescription filled (y/n)
  - If prescribed, has antibiotic been taken (y/n, # doses)
  - If antibiotics taken, were any side-effects noted (y/n, list)
  - Increased or decreased pain (y/n, increased/decreased)
  - Increased or decreased size of redness (y/n, increased/decreased)
  - Any new symptoms? (y/n, list) Specific questions will include: presence of rash, loose stool, nausea, vomiting, abdominal discomfort, headache, dizziness, drowsiness, thrush, as well as any change in local signs or symptoms including pain and redness, new skin lesions, enlarged lymph nodes, and sore or white spots in the mouth.

Visit 2 - Day 3 -1/+2: (ED)

Subjects' wound status will be evaluated. The following information will be collected and recorded on a hard copy Case Report Form at this visit:

- Questions about infection
  - Infection overall (better/same/worse)
  - Fever > 38°C at home since incision? (y/n)
  - Persistent discharge (y/n)
  - Pain (increased/same/decreased/resolved)
  - Medical evaluation between day 1 and day 3 visit (y/n)
  - New lesions (y/n)
  - Was an p.o. antibiotic prescribed (y/n)
    - If yes, was the prescription filled (y/n)
    - How many doses have been taken so far? (##)
  - Any diarrhea? (y/n)
  - Any nausea or vomiting? (y/n)
  - Any abdominal discomfort? (y/n)
  - Any new rash? (y/n)
  - Any other new symptoms including headache, dizziness, drowsiness, thrush, as well as any change in local symptoms.
  -
- Bacterial burden in wound bed – Wound culture performed using quantitative methods for culturing wound base (Gardner, Frantz et al. 2006). Cultures taken to [name] lab for quantitation, swab may be stored at 4°C, if obtained after business hours.
  - Quantitation of bacteria present (colony counts performed in [name] lab)
  - Speciation of bacteria present (CHKD clinical microbiology laboratory using CLSI standards)
  - Antibiotic susceptibility testing of bacteria present (CHKD clinical microbiology laboratory using CLSI standards)
- Wound assessment
  - Fever > 38°C in ED? (y/n, record temp)
  - Packing present (y/n)
  - Erythema at widest diameter (mm)

- Abscess induration at widest diameter (mm)
    - Tenderness around the wound? (y/n)
    - Removal of packing

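### Half of the randomized subjects are expected not to complete, yet the SAP sets no side-effect denominator, and a subject who misses Visit 2 has no stated late safety contact

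*Combined protocol and SAP*

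**What the plan says.** **Expected loss.** The Study Size paragraph plans 100 randomized subjects, allocated 2:1, and continues: "We anticipate 50 participants completing the study". It adds: "The 50% retention rate is typical for emergency department populations". The Primary Endpoint section makes the comparison of safety and side effects with standard care the main purpose.

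**Analysis rule.** The Statistical Analysis Plan has one sentence on incomplete follow-up: "Patients who withdraw while on treatment will be included in the data analysis for each time point before withdrawal". It lists safety among the measurements to be summarized descriptively. A later paragraph describes equivalence testing of outcomes, without naming them and without a numeric margin.

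**Symptom contacts.** The Study Treatments section asks about side effects at four points:
- a call on Day 2 (+2);
- Visit 2 in the ED on Day 3 (-1/+2);
- a call on the day before the CHKD clinic visit;
- Visit 3 at CHKD on Day 7 ± 2.

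Booking the CHKD visit is an item of Visit 2, and the Study Visit Schedule marks the second call in the Visit 2 column. Stopping Rules, writing about subjects with an adverse reaction or SAE, lists a Day 6 telephone contact as part of scheduled follow-up.

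**Other capture.** Under Recruitment and Retention, a medical release is obtained so that "outcomes data can be collected related to additional unscheduled visits or adverse events cared for outside the emergency department setting".

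**The concern.** The SAP rule works per time point and covers withdrawal during treatment. It does not say what happens to a subject who just stops coming, which is the likely form of loss in an ED population. It also does not define the percentage of subjects with a side effect across four contacts. Candidate denominators are all randomized, all packed, everyone contacted at least once, and completers. With half the sample expected to be incomplete, these can give materially different answers.

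Late data are also less secure than they look. The second checklist call depends on an appointment made at Visit 2, and nothing says what happens to the call when Visit 2 is missed. Both arms have something to lose:
- The Adverse Reaction paragraph singles out local reactions at the packed wound. In the TheraGauze arm the packing is due to come out at Visit 2, so a subject who misses that visit can have a later local reaction that nobody asks about.
- In the control arm, physicians may prescribe an oral antibiotic. The Background describes usual practice as "anti-MRSA systemic antibiotics given orally for 5 – 7 days", so side effects can appear after the first call.

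The release recovers events that led to care elsewhere. It does not recover mild events for which no care was sought. A contact not made during the trial cannot be fully reconstructed at analysis.

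**Working it through.** **1. The plan's own figure.** Completers = 100 × 0.50 = 50; equivalently 50/(1 − 0.50) = 100. The stated numbers agree. The 2:1 split gives about 67 and 33 randomized and, if retention is equal by arm (assumption), about 33 and 17 completing.

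**2. Timeline for a subject who misses Visit 2.** The first call falls on Day 2 to 4. The Visit 2 window is Day 2 to 5. If it is missed, no CHKD visit has been booked, so the day-before call has no anchor. If an antibiotic course starts on Day 1 (assumption) and lasts 5 to 7 days, it ends on Day 5 to 7. That leaves 1 to 3 days of the course after a Day 4 call, or 3 to 5 days after a Day 2 call.

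**3. The second call is not a fixed Day 6 call.** Visit 3 on Day 7 ± 2 means Day 5 to 9, so the call falls on Day 4 to 8. Only a Day 7 visit puts it on Day 6, as Stopping Rules has it.

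**4. Effect of the denominator alone.** Assume completer rates of 10% (TheraGauze) and 20% (control).
- Among completers: 10% − 20% = −10 points.
- Over all randomized, with unseen subjects taken as event-free: 0.10 × 33/67 = 4.9% and 0.20 × 17/33 = 10.3%, a difference of −5.4 points.

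**5. Logical bounds on that difference, with nothing known about non-completers.**
- TheraGauze: 3.3/67 = 4.9% to (3.3 + 34)/67 = 55.7%.
- Control: 3.4/33 = 10.3% to (3.4 + 16)/33 = 58.8%.
- Difference: 4.9 − 58.8 = −54 points to 55.7 − 10.3 = +45 points.

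**6. Direction.** Let the true rate be 20% in both arms, and let subjects with an event be r times as likely to complete as those without. The completer rate is 0.20r/(0.20r + 0.80).
- r = 0.5 gives 0.10/0.90 = 11.1%.
- r = 1 gives 20%.
- r = 1.5 gives 0.30/1.10 = 27.3%.

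With r = 0.5 in the TheraGauze arm only, the apparent difference (TheraGauze minus control) is −8.9 points. With r = 0.5 in the control arm only, it is +8.9 points. The true difference is zero in both cases.

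**7. Scale against sampling error.** The half-width of the 90% interval at 20% in both arms is 1.645 × √(0.16/67 + 0.16/33) = 14 points with everyone observed, and 1.645 × √(0.16/33 + 0.16/17) = 20 points with completers only.

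**8. What reaching more subjects buys.** For an observed rate of 20% and a share m missing, the true rate lies between 0.20(1 − m) and 0.20(1 − m) + m:
- m = 50%: 10% to 60%;
- m = 25%: 15% to 40%;
- m = 10%: 18% to 28%.

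**The case against.** This is a Phase I pilot whose control arm is there to give some comparative data, and safety is to be summarized descriptively. The SAP sentence already points to available data at each time point, not to counting absence as no event. Only subjects who miss Visit 2 lose the trigger for the second call: those who attend it and skip Visit 3 are booked and due the call, and the documents do not split the 50%. The first call doubles as a reminder and carries the full checklist. Stopping Rules mentions a Day 6 contact, and Roles of Research Team Members gives coordinators a general duty to telephone. All of this stands. It narrows the gap, but it does not supply a denominator, a rule for subjects lost without withdrawing, or a late contact after a missed Visit 2.

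A reader might infer more, in four ways that the documents do not support:
- **The comparison is pushed toward similarity, or false equivalence becomes more likely.** That needs a margin, a statement that side effects are tested for equivalence, or a rule that lost subjects are event-free. The plan contains none of these. If loss is unrelated to events and completers are analysed, the main effect is lost precision, which generally works against concluding equivalence.
- **The gap falls mainly on the control arm.** Antibiotics there are optional, no share is given, and the course length is a background description of usual care. Late local reactions can be lost in the TheraGauze arm too.
- **Half of the sample has no late information.** Non-completion is not the same as no contact.
- **No late call was meant for subjects who miss Visit 2.** The Day 6 wording suggests one was intended; what is missing is a stated trigger.

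**Conclusion.** The point holds as a cheap improvement worth making. Half of the randomized subjects are expected not to complete, the primary endpoint is a side-effect comparison, and the plan neither defines its denominator nor bounds the effect of loss. As written, a subject who misses Visit 2 has no stated late side-effect contact.

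The comparison may be biased, but the documents do not allow its size or direction to be determined. They give no retention by arm or by event status, no timing of losses and no share of controls prescribed antibiotics. The illustrations rest on assumed event rates, equal retention by arm and assumed completion ratios. They show that the choice of denominator can roughly halve a difference (−10 to −5.4 points). They also show that event-related loss in one arm can move a null difference by 8.9 points either way, against a 90% half-width of 14 to 20 points. The bounds at 50% missing are an upper limit on the uncertainty, because the first call and the release recover some events.

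**What to change.** 1. **Contact.** Reconcile the Study Treatments text, Stopping Rules and the Study Visit Schedule. Keep the day-before reminder call for subjects with a booked CHKD visit. Make the same checklist call on or just after Day 7 to every randomized subject who has no booked visit or did not attend Visit 3. This leaves the reminder in place and covers the period through Day 7. The means exist: at Visit 1, "Contact Information to include phone number(s), address, and primary care provider information will be collected".
2. **Denominator.** State in the SAP that side effects through Day 7 are reported by assigned arm in all packed subjects, using calls, visits and records obtained under the release.
3. **Missing information.** Report by arm the number with no late information and do not count them as event-free. Show the available-case result with best/worst-case or tipping-point bounds.

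**Cost.** A few lines of protocol text, a short SAP paragraph and modest coordinator time. If completing means attending Visit 3, this is at most about 100 − 50 = 50 subjects to call. Telephone data are less detailed than a clinic assessment, especially for wound findings, and the bounds stay wide if many subjects cannot be reached.

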    - Does wound require repacking? (y/n)
- Clinical Options
  - Return to ED for additional clinical evaluation and management (y/n)
      - Reason for reevaluation (infxn worsening/infxn non-improvement/other)
      - Another incision and drainage in the ED (y/n)
      - Addition of oral antibiotics (y/n)
      - Admission for i.v. Abx (y/n)
      - Admission for surgical intervention (y/n)
      - Return to ED in 2 more days (y/n)
- Schedule follow-up visit in Infectious Diseases Clinic at Children's Hospital of The King's Daughters (CHKD) in  $5 \pm 2$  days

Phone Follow up Contact Day Prior to CHKD visit:

Return visit reminder performed by Study Coordinator.

- Fever since leaving ED? (y/n, record temp if taken)
  - If prescribed, has antibiotic been taken (y/n, # doses)
  - If antibiotics taken, were any side-effects noted (y/n, list)
  - Increased or decreased pain (y/n, increased/decreased)
  - Increased or decreased size of redness (y/n, increased/decreased)
  - Any new symptoms? (y/n, list) Specific questions will include: presence of rash, loose stool, nausea, vomiting, abdominal discomfort, headache, dizziness, drowsiness, thrush, as well as any change in local signs or symptoms including pain and redness, new skin lesions, enlarged lymph nodes, and sore or white spots in the mouth.

Visit 3 - Day  $7 \pm 2$ : (CHKD Infectious Diseases Clinic):

Follow up on subjects' wound status. The following information will be collected and recorded on a hard copy Case Report Form at this contact.

- Questions about infection
  - Fever  $> 38^{\circ}\text{C}$  at home since incision? (y/n)
  - Pain (increased/same/decreased/resolved)
  - Redness (increased/same/decreased/resolved)
  - Persistent discharge (y/n)
  - Wound size (increased/same/decreased/resolved)
    - If resolved, day of wound closure (day)
  - New lesions since day 3 visit (y/n)
  - Was an p.o. antibiotic prescribed (y/n)
    - If yes, was the prescription filled (y/n)
    - How many doses have been taken so far? (##)
  - Any diarrhea? (y/n)
  - Any nausea or vomiting? (y/n)
  - Any abdominal discomfort? (y/n)
  - Any new rash? (y/n)

- Any other new symptoms including headache, dizziness, drowsiness, thrush, as well as any change in local symptoms.
- Wound assessment
  - Fever > 38°C in CRU? (y/n, record temp)
  - Packing present (y/n)
  - Diameter of erythema (mm) at widest diameter
  - Diameter of wound (mm) at widest diameter
  - Tenderness around the wound? (y/n)

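### If continuous wound measures enter the SAP's 90% CI, it should prespecify adjustment for the Visit 1 erythema and induration already collected; it now names neither the measures nor a covariate

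*Combined protocol and SAP*

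**What the plan says.** The Statistical Analysis Plan section has two relevant parts.

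- **Description.** The list of what is summarised opens with "Baseline and follow-up measurements of safety, tolerability, numbers of pathogenic bacteria, wound infection persistence or worsening" and ends by saying that "gross effects on the rate of wound healing will be summarized using descriptive statistics". That sentence plans summary statistics only; it contains no contrast between arms and no interval.
- **Inference.** The next paragraph begins "Tests of equivalence between the TheraGauze + tobramycin and standard iodoform wick packing treatment groups will establish statistical significance if the two-sided 90% confidence" and makes the criterion that the "interval for the difference falls within the limits" of plus or minus delta. Delta "is the margin of clinically accepted difference" and has no numerical value. The purpose is stated as "This analysis will determine whether the outcomes are equivalent between the TheraGauze+tobramycin and standard iodoform wick packing treatment groups". The outcomes are not listed, and the text does not say whether the difference is in follow-up values, in change from baseline, or from a model. No covariate is named.

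The case report form items under Study Treatments show what is available, in mm:

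| Measure | Visit 1 | Visit 2 | Visit 3 |
|---|---|---|---|
| Erythema | yes | yes | yes |
| Induration | yes | yes | not listed |
| Wound diameter | after incision | not listed | yes |

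Erythema is the item that begins "Erythema at widest diameter (mm" at Visits 1 and 2, and "Diameter of erythema (mm) at widest diameter" at Visit 3.

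**The concern.** Entry size is likely to vary widely. Subject Eligibility sets a minimum induration of 2 cm with no maximum, and allows cellulitis up to 6 cm beyond the induration. Study Size anticipates only 50 completers, split 2:1. If follow-up erythema or induration is compared without using the Visit 1 value, both the spread in entry size and any chance imbalance in it pass into the estimated difference and its interval. An equivalence conclusion requires the whole interval to lie inside the margin, so unnecessary width makes that conclusion harder to reach.

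Erythema also has some bearing on safety: the Adverse Reaction definition treats worsening redness at the packed wound as a possible sign of local toxicity. If the estimator is left open until data are in hand, the choice of covariate can also be influenced by the results.

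**Working it through.** **Inputs from the documents.** Study Size gives 100 randomised, 2:1 allocation, 50% retention and 50 completers. The SAP gives a two-sided 90% CI.

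**Check of the plan's own figure.** 50 / (1 − 0.50) = 100, which agrees with the stated 100. The documents give no power calculation, SD, effect size or interval width to reproduce.

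**Group sizes.** Two-thirds and one-third of 50 is about 33 v 17; of 100 it is about 67 v 33. The SAP keeps withdrawn patients in the analysis for time points before withdrawal, so Visit 2 can have anywhere from about 50 to 100 subjects. Thus 33 v 17 is the low end for Visit 2, and 67 v 33 is its upper bound.

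**Assumed input.** The correlation r between the Visit 1 and follow-up value of a measure is not in the documents. I use r = 0 to 0.7. Results are in units of the follow-up SD.

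**Formulas for the 90% half-width.**

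- Unadjusted: t(0.95, N − 2) × √(1/n1 + 1/n2)
- Adjusted for Visit 1: t(0.95, N − 3) × √[(1/n1 + 1/n2)(1 − r²)(1 + 1/(N − 4))]. The last factor is the average small-sample cost of estimating the slope.
- Change from baseline, equal SDs: unadjusted half-width × √[2(1 − r)]

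**Numbers for 33 v 17.** √(1/33 + 1/17) = 0.2985. Unadjusted: 1.677 × 0.2985 = 0.501. Adjusted at r = 0.5: 1.678 × 0.2985 × √(0.75 × 1.0217) = 0.439.

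| r | 33 v 17 adjusted (unadjusted 0.501) | Ratio | 33 v 17 change score | 67 v 33 adjusted (unadjusted 0.353) | Ratio |
|---|---|---|---|---|---|
| 0 | 0.506 | 1.011 | 0.708 | 0.355 | 1.005 |
| 0.3 | 0.483 | 0.965 | 0.592 | 0.339 | 0.959 |
| 0.5 | 0.439 | 0.876 | 0.501 | 0.307 | 0.871 |
| 0.7 | 0.362 | 0.722 | 0.388 | 0.254 | 0.718 |

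The adjusted interval is also narrower than a change-score interval at every r shown, so the point does not depend on which unadjusted difference the SAP intends.

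**Break-even.** Adjustment pays on average once √(1 − r²) falls below 1/1.011 at 33 v 17, which is r of about 0.15. At 67 v 33 it is about 0.10.

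**Simulation.** In 10,000 simulated trials per value of r at 33 v 17, the mean ratio of adjusted to unadjusted width was 1.011 at r = 0, 0.966 at 0.3, 0.878 at 0.5 and 0.726 at 0.7, close to the formula. The adjusted interval was the wider of the two in 79% of trials at r = 0, 48% at 0.2, 24% at 0.3 and 2% at 0.5.

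**The case against.** The strongest objection is that the SAP commits to no unadjusted wound-healing comparison at all. A reader might infer that it reports raw between-arm differences in erythema, induration and wound size, so that every wound-healing interval is wider than it needs to be. The documents do not support that. The SAP names none of these measures, its wound-healing sentence is descriptive, and the CI paragraph leaves the difference undefined. The gain depends on a correlation that is nowhere given and vanishes below about 0.15 at 50 completers. Categorical items, such as the Visit 3 report of wound size as increased, same, decreased or resolved, have no Visit 1 counterpart to adjust for. This part of the objection stands, and it makes the point conditional.

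Three further limits also stand.

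- This is a Phase I pilot whose Primary Endpoint is safety and side effects. The missing outcome list and the missing value of delta are larger gaps in the same paragraph. With neither delta nor an SD given, the effect on any equivalence decision cannot be calculated.
- Visit 1 lists randomisation ahead of the case report form items and does not say whether the measurements precede knowledge of the arm. Wound diameter is taken after incision, so it has no clean pre-randomisation counterpart.
- By Visit 3 some wounds will have resolved, and values at or near zero may fit a linear model poorly.

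None of this removes the point. Once the outcomes are named the estimator must still be stated, and the Visit 1 value of the same measure is the obvious covariate.

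**Conclusion.** The point holds conditionally. The SAP's single inferential method names no outcomes, no form of difference and no covariate, although Visit 1 erythema and induration are already recorded. If these measures are tested, adjustment narrows the 90% interval at 33 v 17 by about 3.5% at r = 0.3, 12% at 0.5 and 28% at 0.7, and widens it by about 1% at r = 0. The proportional gain at 67 v 33 is similar. For Visit 3 wound diameter the only candidate free of the incision is baseline induration, a different measure, so the gain there is uncertain.

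These figures assume the stated range for r, a roughly linear relation and a common SD. Leaving out the covariate costs precision; it does not bias the comparison, provided that allocation is properly random and loss to follow-up is not selective. It is a worthwhile, low-risk improvement to a secondary part of the plan and does not undermine the primary safety objective.

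**What to change.** In the Statistical Analysis Plan, before outcome data are seen:

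1. List which outcomes, if any of the continuous wound measures, enter the 90% CI, and give each its delta. This comes first.
2. For erythema at Visits 2 and 3 and induration at Visit 2, if listed, state that the difference and its 90% CI come from a linear model with arm and the subject's own Visit 1 value of that measure.
3. Require the Visit 1 erythema and induration to be recorded before the arm is known, and say so in the Visit 1 procedures.
4. For Visit 3 wound diameter, treat adjustment for baseline induration as optional and decide in advance whether to use it.
5. Extend the planned normality checks to the model residuals, particularly at Visit 3.
6. Keep the unadjusted summaries by arm and visit as description.

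The cost is a few sentences of SAP wording, one instruction on the timing of the Visit 1 measurements and one model per measure and visit. No new data or extra subjects are needed.
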